7.5.3 Questionnaires

Subjective ratings of the test sound processors will be evaluated via paper-based questionnaires.

7.6 Sponsor Role in Conduct of the Clinical Investigation

Sponsor and investigator roles are assumed by Cochlear employees.

This clinical investigation will be conducted by an internal site. Internal sites are clinical research facilities owned and operated by Cochlear. The internal site at Cochlear in Sydney consists of a small team of Investigators, trained as clinical audiologists, to execute this research activity. Investigators are qualified audiologists familiar with cochlear implant development, surgery and programming. Investigators' trial materials, programming and testing rooms (sound booths) are securely separated from Sponsor facilities. The trial investigators, or delegates within the study site, will enter the data into the eCRF.

The study is planned, designed and developed by a separate group within Cochlear, known as Clinical Affairs (the Sponsor). Cochlear has SOPs to manage the separation of Investigator and Sponsor activities as well as ensure they align with all applicable regulations.

Activities to be performed by sponsor representative excluding monitoring include:

- 1. Application of clinical quality assurance and quality control principles to the processes of the clinical investigation
 - a. Implement and maintain written clinical quality procedures to ensure the clinical investigation is designed, conducted and that data generated is compliant with the ISO 14155:2011 Standard (ISO, 2011).
 - b. Clinical quality assurance and quality control will be implemented according to sponsors quality system (Cochlear Quality Manual reference [7])
- 2. Clinical investigation planning and conduct

- a. Selection of clinical personnel for project management of the clinical investigation
- b. Preparation of documents and materials for the clinical investigation
- c. Project management for the clinical investigation. i.e. accountability of investigational devices, clinical trial insurance coverage, submission of application(s) and investigation updates to the appropriate regulatory authority(ies).
- 3. Safety evaluation and reporting of adverse events (AE) to the TGA and ethics committee
- 4. Clinical investigation close-out, statistical analyses and final report

8 RISKS AND BENEFITS OF THE INVESTIGATIONAL MEDICAL DEVICE AND CLINICAL INVESTIGATION

8.1 Anticipated Clinical Benefits

This study provides subjects with the opportunity to trial a new cochlear implant sound processor and related components (Nucleus 8) prior to the commercial release date. Subjects may benefit from improved usability and performance of the different components of the Nucleus 8 system. For subjects who have not previously experienced using the ForwardFocus feature, they may experience benefit of improved communication through reduction of distracting background noise.

Due to the limited use of the IMD (minimum of 4 test blocks over a period of up to 12 months), there are no long-term clinical benefits anticipated for the subjects.

8.2 Anticipated Adverse Device Effects

Cochlear's internal hazards analysis considers probable hazardous situations relating to the Nucleus 7 and Nucleus 8 SPs.

The risks associated with the Nucleus 7 and Nucleus 8 SPs and Accessories have been identified, analysed and evaluated. The residual risk level has been determined to be as low as possible in accordance with Cochlear's Product Risk Management Procedure and are acceptable.

Subjects may be exposed to the anticipated adverse device related effects associated with use of the Nucleus 7 and Nucleus 8 SPs such as pain or discomfort when wearing the processor and a risk that some sounds could be uncomfortable. Product specific warnings can be found in the respective User Guide and relevant instructions for use.

8.3 Risks Associated with Participation in the Clinical Investigation

There is a small risk that the programs on the Nucleus 7 SP and Nucleus 8 SP may sound different to subjects own SP. If subjects experience sound that is uncomfortable they are counselled to remove the sound processor off their head or ask the research audiologist to immediately cease stimulation. Other risks may include exacerbation of existing tinnitus and a reduction in the sound quality or intelligibility of the research programs. Subjects are advised to return to their own processor and promptly inform the investigators if these events occur. Possible interactions with concomitant medications and residual risks for the device are not anticipated in this clinical investigation.

Clinical Investigation Plan | VV-TMF-06258 | 2.0 Approval Date (GMT+0): 31 Aug 2021

CIP Number: CLTD5810

See the Nucleus 7 SP User Guide for all Warnings and Contraindications. (user guides can be found within the 'Support' section of the country specific Cochlear website; ________). At this preliminary stage in development, the Nucleus 7 SP User Guide will be relevant for Nucleus 8 SP.

As the study procedures involve planned visits to the Cochlear headquarters research site, there may be an increased risk of contracting infectious diseases such as COVID-19 whether in transit to the site or moving throughout the building.

8.4 Risk Mitigation

The study investigational devices have been tested for safety, and the performance and use of the device is expected to be similar to the approved Nucleus 7 SP. Risks have been individually reviewed and found to be clinically acceptable based on implemented controls, verification activities, and the relatively low probability of harm. One or more of the following risk control options are applied to each identified risk: inherent safety by design; protective measures in the device itself or in the manufacturing process; Information for safe usage.

The fitting and use of the CP1110 SP will be managed by the investigator. In cases where the sound becomes at all uncomfortable or uncomfortably loud during fitting, subjects are encouraged to remove the SP from their head or inform the investigator so that stimulation is immediately ceased. Should any such discomfort occur during take-home use, subjects will be advised to remove the CP1110 SP and revert to using their own SP until the cause of the discomfort is understood and resolved.

If subjects experience any physical discomfort from the device or if the device produces sounds that are uncomfortable, subjects are encouraged to inform the Investigator and return to using their own sound processor.

All reported ADEs and DDs will be regularly reviewed by the Sponsor's Clinical review Board for the duration of the study to facilitate early detection and appropriate intervention if events are unanticipated with respect to incidence, severity, or outcome.

Risk mitigation relating to COVID-19

It is expected that study participants will be taking steps to limit exposure to infectious diseases, for example, COVID-19. The site will actively follow the advice of official health authorities and governments to ensure the health and wellbeing of site employees and research subjects. These include but are not limited to:

- Operational changes to ensure attendance at the site is limited to only those who are
 required to be there. Cochlear headquarters has implemented procedures to enable
 contact tracing for all employees and visitors, as well as processes to scale up, scale
 down and/or deep clean should there be a confirmed positive case of the virus on the
 premises.
- The research site is separated physically, enabling separation of study participants from other employees working in the building.
- Increased hygiene etiquette including cleaning of high-touch surfaces before and after each study visit, disinfection of any shared study devices or equipment and investigators are equipped to use gloves or wear a face masks as required. Hygiene

resources such as handwashing/rubbing stations are readily available throughout the building and research site.

- Where possible, study participants will be encouraged to drive to Cochlear and utilise free on-site parking instead of travelling via public transport.
- Subjects will be provided with any necessary resources required to return study devices to the site, should they be unable to attend any of the planned visits. For example, couriers or postage may be arranged as necessary.

8.5 Risk-to-Benefit Rationale

Residual risk levels associated with the CP1110 SP and accessories have been determined to be as low as possible when the sound processor is used with a compatible cochlear implant. The probability of occurrence of harm for all hazards was found to be "remote" or "improbable". Based on pre-clinical testing of the CP1110 SP along with a review of clinical investigations and published data on the Nucleus 7 SP, the anticipated clinical benefits have been found to outweigh the potential risks to the subject through participation in this clinical investigation.

9 STATISTICAL CONSIDERATIONS

9.1 General Considerations

See sections 9.2 to 9.10 for statistical considerations.

9.2 Endpoints

For speech in noise (AuSTIN) endpoints, two lists of sentences will be measured per sound processor condition, and the two dB SRT values will be averaged to produce a single value per condition, per subject.

For speech in quiet (CNC) endpoints, two lists of words will be measured per sound processor condition, and the two percentage words correct values will be averaged to produce a single value per condition, per subject.

For SSQ12 endpoint, one questionnaire which includes 12 questions will be measured per sound processor condition per person. The score is a continuous numeric score, and a single value will be recorded per question.

For the Questionnaires, Nucleus 8 Questionnaires 1 and 2 and the Baseline Questionnaire, the endpoint is the completion of the questionnaire.

9.2.1 Primary Endpoint

The primary efficacy measure for the Nucleus 8 Sound Processor will be Speech Reception Thresholds (SRT) assessed via AuSTIN Sentence scores in spatially separated adaptive noise.

The primary efficacy outcome for the study will be determined by the following primary efficacy endpoint:

• Paired difference in dB SRT (AuSTIN) between the CP1110 Sound Processor with ForwardFocus ON (SCAN) and ForwardFocus OFF (SCAN) (65 dB SPL S0Nrearhalf 4TB).

9.2.2 Secondary Endpoints

- Paired difference in dB SRT (AuSTIN) between the CP1110 Sound Processor with ForwardFocus On (SCAN) and ForwardFocus OFF (SCAN) (65 dB SPL S0N3 Babble).
- Paired difference in percentage CNC Words correct in quiet (50 dB) with the CP1110 Sound Processor and Nucleus 7 Sound Processor
- Paired difference in Global SSQ12 scores after experience with the CP1110 Sound Processor and Nucleus 7 Sound Processor
- Ratings on the 'CP1110 Questionnaire 1' and 'CP1110 Questionnaire 2' after at least 2 weeks of experience with the CP1110 Sound Processor
- Take home use with the CP1110 Sound Processor System

9.2.3 Exploratory Endpoints

Feedback from take home use with the CP1110 Sound Processor System.

9.3 Hypotheses

For the non-inferiority test of SRT sentences for both primary and secondary endpoints, the 95% CI (alpha=0.025 one-sided) for the mean paired difference will be calculated. If the upper limit of the 95% CI of the mean paired difference is lower than 1dB, the treatment condition is regarded as non-inferior to the control on that measure.

For the non-inferiority test of CNC words, the 95% CI (alpha=0.025 one-sided) for the mean paired difference will be estimated. If the lower limit of the 95% CI of the mean paired difference is above - 10%, the treatment condition is regarded as non-inferior to the control on that measure.

For the non-inferiority test of SSQ12 scores, the 95% CI (alpha=0.025 one-sided) for the mean paired difference will be estimated. If the lower limit of the 95% CI of the mean paired difference is above -1, the treatment condition is regarded as non-inferior to the control on that measure.

9.3.1 Primary Hypothesis

Endpoint: Paired difference in dB SRT (AuSTIN) between the CP1110 Sound Processor with ForwardFocus ON (SCAN) and ForwardFocus OFF (SCAN) (65 dB SPL S0Nrearhalf 4TB).

H0: Sentence in noise (S0Nrearhalf 4TB) scores (dB SRT) with the CP1110 Sound Processor with FF On (treatment) are inferior to those with the CP1110 Sound Processor with FF Off (control)

CP1110 FF ON – CP1110 FF OFF ≥ 1 dB (NB: higher SRT scores represent poorer performance)

H1: Sentence in noise (S0Nrearhalf 4TB) scores (dB SRT) with the CP1110 Sound Processor with FF On (treatment) are non-inferior to those with the CP1110 Sound Processor with FF Off (control)

CP1110 FF ON - CP1110 FF OFF < 1 dB

9.3.2 Secondary Hypotheses

Secondary endpoint 1

Endpoint: Paired difference in dB SRT (AuSTIN) between the CP1110 Sound Processor with ForwardFocus On (SCAN) and ForwardFocus OFF (SCAN) (65 dB SPL S0N3 Babble).

H0: Sentence in noise (S0N3 Babble) scores (dB SRT) with the CP1110 Sound Processor with FF On (treatment) are inferior to those with the CP1110 Sound Processor with FF Off (control)

CP1110 FF ON - CP1110 FF OFF ≥ 1 dB

H1: Sentence in noise (S0N3 Babble) scores (dB SRT) with the CP1110 Sound Processor with FF On (treatment) are non-inferior to those with the CP1110 Sound Processor with FF Off (control)

CP1110 FF ON - CP1110 FF OFF < 1 dB

Secondary endpoint 2

Endpoint: Paired difference in percentage CNC Words correct in quiet (50 dB) with the CP1110 Sound Processor and Nucleus 7 Sound Processor

H0: Words in quiet (50 dB CNC words) scores (% words correct) with the CP1110 Sound Processor (treatment) are inferior to those with the Nucleus 7 Sound Processor

CP1110 - Nucleus 7 < -10%

H1: Words in quiet (50 dB CNC words) scores (% words correct) with the CP1110 Sound Processor are non-inferior to those with the Nucleus 7 Sound Processor

CP1110 - Nucleus 7 > -10%

Secondary endpoint 3

Endpoint: Paired difference in Global SSQ12 scores after experience with the CP1110 Sound Processor and Nucleus 7 Sound Processor

H0: Hearing performance ratings (SSQ12) with the CP1110 Sound Processor (treatment) are inferior to those with subject's own processor (control)

CP1110 - Nucleus 7 ≤ -1

H1: Hearing performance ratings (SSQ12) with the CP1110 Sound Processor (treatment) are non-inferior to those with subject's own processor (control)

CP1110 - Nucleus 7 > -1

There are not hypotheses for the following endpoints;

- Ratings on the 'CP1110 Questionnaire 1' and 'CP1110 Questionnaire 2' after at least 2 weeks of experience with the Nucleus 8 Sound Processor
- Take home use with the CP1110 Sound Processor System

9.3.3 Exploratory Hypothesis

There are no exploratory hypotheses

9.4 Sample Size Determination

This study is a non-inferiority design, and sample size calculation was based on non-inferiority tests for SRT (Speech Recognition Threshold) scores and CNC word scores. The sample size using a confidence interval method (one-tailed 97.5% confidence interval) was estimated to have a reasonable power to detect non-inferiority of sentence and word scores for the above-mentioned hypotheses.

To reject the null hypothesis of inferior sentence in noise scores (SRT scores), the following parameters for sample size calculation were chosen:

- A clinical important difference value of 1 dB SRT. This margin is based on clinical consensus.
 NB: higher SRT scores represent poorer performance.
- A standard deviation (SD) of change or difference scores of 1.36 dB. This SD is calculated from 256 paired differences and is an indicative test re-test SD for both S0N3 and S0N0.
- A significance level α = 0.025 (one-tailed).
- A desired power of 0.8

Based on these assumptions, a sample size of 17 are required to reject the null hypotheses. Twenty subjects will be enrolled to allow for any unforeseen subject withdrawal.

9.5 Analysis Populations

The analysis of the primary endpoint will be based on the Intent-To-Treat (ITT) and Per Protocol (PP) analysis populations in order to support a conclusion of non-inferiority. The inclusion of both ITT and PP populations has been chosen to assess the robustness of the study results and the consistency of the study measures under different analysis populations.

This study has a non-inferiority design; therefore the primary analysis will be based on the PP population.

For cases in which the ITT and PP populations lead to the same conclusions and final interpretations about the treatment effect, the results will be considered to not be influenced by underlying factors such as missing data and protocol deviations, and the results would be considered to be robust and consistent under different analysis populations. A statement to reflect this will be included in the CIR.

For cases in which the ITT and PP populations lead to different final interpretations or conclusions, all of the results will be reported and the differences in outcomes will be identified and explored.

Intent-to-Treat Population

The Intent-to-Treat Population will include all subjects who receive the treatments and have at least one set of paired treatment and control measurements from any endpoint, regardless of protocol deviations and missing data.

Per Protocol Population

The Per Protocol Population will include all subjects who receive the treatments and have at least one paired measurements from treatment and control, without major protocol deviations. Major deviations will be defined at the clean file meeting before data base lock.

It is possible that a treatment has not been administered in the intended counterbalanced order of presentation. It is also expected that the sequence and period effects are minimal in this study if any. This study is not a full cross-over design, so period and sequence effects will not be assessed, without the consequence to bias the study conclusion.

Safety Population

The Safety Population will include all treated subjects. The Safety Population will be used for the safety data analysis.

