7.2.6 Criteria for Subject Withdrawal

Subjects can decide to withdraw from the investigation at any time and are not obliged to provide any justification for their decision. The Investigator shall ask the reason(s). The reason for withdrawal should be documented in the subject's source files and the case report form (CRF).

The Investigator or Sponsor may also decide to withdraw a subject from the clinical investigation if it is considered to be in the subject's best interests.

Subject withdrawal may be for any of the following reasons:

- Adverse Event (AE)
- Device Deficiency (DD)
- CIP or GCP deviation
- Subject withdrew consent
- Subject lost to follow-up
- Subject death
- Sponsor decision
- Investigator decision

If a subject is lost to follow-up, every possible effort must be made by the study site personnel to contact the subject and determine the reason for discontinuation. At least 3 separate attempts taken to contact the subject must be documented.

Participating subjects who are withdrawn/discontinued will not be replaced.

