9.6 Primary Endpoint Analyses

Primary and Secondary Speech Perception Endpoints:

SRT sentence scores in noise and words in quiet scores at different speech testing conditions will be listed and summarised descriptively by treatment group and study population. A Scatter plot or similar plot will be used to present the individual data by treatment group, and bar chart will be used to present the average paired difference and its standard error.

For the non-inferiority test of SRT sentence scores the 95% CI (alpha=0.025 one-sided) for the mean paired difference will be estimated. If the upper limit of the 95% CI of the mean paired difference is lower than 1dB, the treatment condition is regarded as non-inferior to the control in term of SRT sentence perception. The non-inferiority margin of 1dB for SRT is based on clinical consensus.

The same analysis method will be applied to the non-inferiority test for words in quiet scores (monosyllables). For the non-inferiority test of words in quiet scores, the 95% CI (alpha=0.025 one-sided) for the mean paired difference will be estimated. If the lower limit of the 95% CI of the mean paired difference is above -10%, the treatment condition is regarded as non-inferior to the control in term of words in quiet perception. The non-inferiority margin of -10% for words in quiet scores (monosyllables) is also based on clinical consensus.

Only when the non-inferiority test for the above specified endpoint is successful, then a superiority test for the endpoint will be further conducted to assess the treatment effect.

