13 DEVIATIONS FROM THE CLINICAL INVESTIGATION PLAN

The Investigator(s) must not deviate from the CIP, except in case of an emergency to protect the safety and well-being of the subject(s). Such deviations will be documented by the site personnel in the source documentation for the subject and reported to the relevant EC as per institutional

Clinical Investigation Plan | VV-TMF-06258 | 2.0 Approval Date (GMT+0): 31 Aug 2021

CIP Number: CLTD5810

requirements and to the Sponsor as soon as possible, but not later than 5 working days from the date of the emergency.

If there is a deviation from CIP-defined assessments or parts thereof are omitted or completed incorrectly, the deviation will also be documented by the site personnel in the source documentation for the subject. Depending on the type or severity of the deviation the Investigator may be required to notify the EC, particularly if the deviation potentially impacts subject safety, performance of IMD and/or comparator, or data integrity.

All CIP deviations will be documented in the eCRF to enable analysis and reporting by the Sponsor in the Clinical Investigation Report (CIR), or to the relevant regulatory authority(s), if applicable.

Gross misconduct on behalf of an Investigator, such as intentional non-compliance with CIP or GCP requirements or fraud, will result in disqualification of the Principal Investigator and/or Investigational Site from participation in the investigation. Data provided by the Principal Investigator or Investigational Site will be excluded from the per-protocol analysis group.

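### Agreement between ITT and PP is read as showing that missing data had no influence, but a subject with no S0Nrearhalf pair enters neither estimate

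*Combined protocol and SAP*

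**What the plan says.** Section 9.5 analyses the primary endpoint in two populations, with PP as the primary one. ITT consists of treated subjects who "have at least one set of paired treatment and control measurements from any endpoint, regardless of protocol deviations and missing data". PP requires at least one treatment and control pair and no major deviation; major deviations are to be defined at the clean file meeting before database lock.

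If the two populations lead to the same conclusion, "the results will be considered to not be influenced by underlying factors such as missing data and protocol deviations". The section adds: "A statement to reflect this will be included in the CIR".

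The estimator is in section 9.6: "For the non-inferiority test of SRT sentence scores the 95% CI (alpha=0.025 one-sided) for the mean paired difference will be estimated". Section 9.3 says the same. Neither section, nor any other, gives an imputation rule, a model for incomplete data or a sensitivity analysis for missing data.

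The plan allows for losses. Section 9.4 requires 17 subjects and states: "Twenty subjects will be enrolled to allow for any unforeseen subject withdrawal". Section 7.2.6 states: "Participating subjects who are withdrawn/discontinued will not be replaced".

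**The concern.** Comparing two analysis sets can reveal the influence of missing data only if subjects with missing data contribute differently to the two sets. Here they do not. A subject without an S0Nrearhalf pair has no paired difference. That subject may be in ITT through another endpoint, such as SSQ12, but still adds nothing to the ITT mean for the primary endpoint, and nothing to the PP mean.

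At stake is a prescribed statement in the report of a pivotal study. Followed as written, the rule has the CIR tell readers that missing data did not influence the result, on the strength of a comparison that cannot examine wholly missing pairs.

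**Working it through.** **What agreement can and cannot show**

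- *Pair present, major deviation:* the subject is in the ITT estimate and not in the PP estimate. Agreement is informative about deviations.
- *Pair incomplete:* section 9.2 says "two lists of sentences will be measured per sound processor condition", so one list may be absent. Section 13 covers the case "If there is a deviation from CIP-defined assessments or parts thereof are omitted or completed incorrectly". The subject's value can differ between the two estimates only if the omission is classed as a major deviation. Agreement is then informative, through the deviation route.
- *Pair wholly absent:* the subject is in neither estimate. Classing the missed test as a major deviation changes nothing, because removing a subject who supplies no value leaves the mean unchanged. If such pairs are the only departure, both estimates come from the same subjects and agree by construction.

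**The plan's own figure**

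Inputs from section 9.4: margin 1 dB, SD of differences 1.36 dB, one-sided alpha 0.025, power 0.80. The true difference is not stated; I assume 0 dB. A paired t-test (noncentral t) gives power 0.785 at n = 16 and 0.812 at n = 17, so the stated 17 is reproduced. Enrolling 20 leaves room for 3 losses.

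**How unfavourable would the missing differences have to be?**

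Assumptions: 20 participating subjects and no PP exclusions among those with a pair. The SD is 1.36 dB, which section 9.4 calls indicative for S0N3 and S0N0, not for S0Nrearhalf. The documents give no expected mean and no expected number missing, so ranges are shown.

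Let n₁ = 20 − k pairs be observed with mean m and SD s, and let the k missing differences (ForwardFocus ON minus OFF) all equal d. Then

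- mean of all 20 = (n₁m + kd)/20
- sum of squares = (n₁ − 1)s² + (n₁k/20)(d − m)²
- upper limit = mean + t(0.975, 19) × √(sum of squares/19)/√20

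Set the upper limit to 1 dB and solve for d.

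Example with k = 3, m = 0, s = 1.36, d = 2.095:

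- mean = 3 × 2.095/20 = 0.314
- sum of squares = 16 × 1.8496 + 2.55 × 4.389 = 29.59 + 11.19 = 40.79
- SD = √(40.79/19) = 1.465
- upper limit = 0.314 + 2.093 × 1.465/√20 = 0.314 + 0.686 = 1.00 dB

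Tipping value d, in dB, at SD 1.36:

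| Pairs missing | m = +0.2 | m = 0 | m = −0.5 | m = −1.0 |
|---|---|---|---|---|
| 3 | 1.40 | 2.10 | 3.50 | 4.72 |
| 2 | 1.77 | 2.77 | 4.79 | 6.56 |
| 1 | 2.73 | 4.47 | 7.93 | 11.00 |

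With 3 missing, the upper limit from the 17 observed pairs is 0.90, 0.70, 0.20 and −0.30 dB across the columns, so non-inferiority is declared in each case. For m = 0, −0.5 and −1.0 the tipping values lie 1.5, 2.9 and 4.2 SD above the observed mean; for one missing pair they lie 3.3, 6.2 and 8.8 SD above it.

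Changing the SD, with 3 missing and m = 0, −0.5, −1.0: SD 1.0 gives 2.57, 3.81, 4.95 dB; SD 1.7 gives 1.50, 3.12, 4.44 dB.

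**Does the comparison of populations react?**

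With 17 pairs and m = 0 the ITT upper limit is 0.70 dB. If PP drops one or two further subjects and the mean and SD stay the same, its limit is 0.73 or 0.75 dB. Both conclude non-inferiority whatever the three missing values were.

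**The case against.** The strongest case is that little harm is likely. ForwardFocus ON and OFF are two programs on the same Nucleus 8 (section 5.2, Table 2), all comparisons for an endpoint are made on one day (section 7.3.7), and the test order is not revealed to the subject (section 7.2.7.1). A missing pair would mostly be a missed session with no stated link to the ON−OFF difference. If missingness were unrelated to outcome and differences were normal, three subjects would average about 1.5 SD above the mean only about 0.4% of the time. Section 9.10 also expects a complete primary data set, and earlier studies summarised in section 4.2.2 reported a benefit of ForwardFocus in rear noise. All of this stands and limits the practical weight of the point. But these are arguments from the design. The plan rests its statement on ITT/PP agreement, which does not supply them.

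Second, the plan already lists scores and plots individual data (section 9.6), and records withdrawal reasons (7.2.6), subject status (14) and omitted assessments (13). Absent pairs would therefore be traceable. That is true, but a listing does not show whether absent pairs could change the conclusion.

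Third, deleting the words on missing data might discard the valid part, namely incomplete tests. It does not: incomplete tests classed as major deviations remain covered by the words on protocol deviations, and incomplete tests not so classed are not examined by the comparison anyway.

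The point does not depend on when the speech tests take place. A subject without a pair drops out of both estimates under any timing.

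**Conclusion.** The concern holds. The agreement rule in section 9.5 is invalid for wholly missing S0Nrearhalf pairs, because neither estimate contains those subjects. This rests on there being no missing-data method for the primary endpoint, and none is stated.

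No bias in the primary result is shown, and the primary test, margin and sample size are unaffected. If every participating subject supplies a pair, the rule does no harm. Under the assumptions above, the conclusion is sensitive only if several pairs are missing and the observed mean is near or above 0 dB: with 3 missing, tipping values of 1.4 dB at m = +0.2 and 2.1 dB at m = 0. With an observed benefit of 0.5 to 1 dB it is sturdy, at 3.5 to 4.7 dB. The rule should be changed because it prescribes an unsupported statement in the CIR.

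**What to change.** 1. In section 9.5, take missing data out of the agreement rule and out of the CIR statement it triggers, so that agreement supports robustness to protocol deviations only.
2. Report the number of participating subjects (as defined in section 7.2.5) without an S0Nrearhalf pair, with the reason and timing for each.
3. If any pair is missing, add one simple sensitivity analysis. A tipping-point table would do, giving the ON−OFF difference in those subjects at which the upper 95% limit reaches 1 dB.

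The cost is a wording change and at most one table, and the CIR robustness statement becomes narrower. Withdrawal reasons and subject status are already collected, so no new data are needed. The primary test and its power are unchanged. If no primary pair is missing, no table is needed.
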